9.3.2 Analysis of Safety

No statistical analysis of safety data will be performed in this study. Safety will be assessed using the SAS with subjects included in the treatment group they actually received, regardless of their randomized treatment. The assessment of safety will include adverse events, clinical laboratory assessments, ECGs, physical examinations, and vital signs. Observed case data will be used.

Adverse events (AEs) will be coded using the most recent version of the Medical Dictionary for Regulatory Activities (MedDRA). The summarization of AEs will include only treatment-emergent AEs (TEAEs), defined as AEs that begin or worsen after randomization and ingestion of the first dose of study drug. TEAEs and SAEs will be summarized by system organ class (SOC), severity, and relationship to study drug for each treatment group. Deaths, withdrawal from study treatment due to AEs, and withdrawal from the study due to AEs will each be summarized by treatment group.

Safety laboratory data will be summarized by treatment group at baseline and at each post-baseline time point. Change from baseline to each time point, if appropriate, will also be summarized by treatment group. Baseline for safety laboratory data will be defined as the last pre-dose measurement (pre-dose Study Day 1/Visit T1 or prior). Frequency counts of new or worsening abnormalities will also be provided.

Vital signs data (value and change from baseline, where appropriate) will be summarized by treatment group at baseline and at each post-baseline time point. Baseline for vital signs data will be defined as the last pre-dose measurement (pre-dose Study Day 1/Visit T1 or prior). Abnormalities in ECGs and in PEs will be summarized.

All safety data will be listed.

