Phase 1 pharmacokinetic (PK) studies have demonstrated that gemcabene is rapidly absorbed following oral administration, with exposure increasing approximately linearly with dose. No clinically meaningful drug-drug interactions have been observed with simvastatin (80 mg), atorvastatin (80 mg), or digoxin (0.25 mg). No clinically relevant effect on QTc or blood pressure has been observed.

Across all clinical studies, the majority of treatment-emergent adverse events were mild to moderate in intensity. The most common adverse events reported included headache, asthenia (feeling of weakness), nausea, dizziness, dyspepsia (upset stomach), infection, abnormal bowel movements, myalgia, and abnormal kidney function tests. Ten healthy adult subjects reported a treatment-emergent serious adverse event (SAE) across all previous studies. None of these SAEs were considered treatment-related. There were no deaths.

Small mean increases in serum creatinine and blood urea nitrogen (BUN) have been observed in some studies. These changes appeared within the first 2 to 4 weeks and did not appear to increase further over time. An iohexol clearance study showed that glomerular filtration rate (GFR) decreased slightly and was associated with a slight increase in serum creatinine. There was no indication of proteinuria or hematuria identified in any subject. There were no significant changes observed in urine protein, which seems to indicate that gemcabene does not cause tubular or glomerular injury. And, the increase was reversible with all creatinine values returning to baseline within approximately 2 weeks of cessation of gemcabene, suggesting a vascular effect and not renal injury.

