The duration of the Treatment Period will be 12 weeks. Eligible subjects will be randomized via an interactive web/voice response system (IWRS/IVRS) on Day 1 in a 1:1 ratio to the following treatment groups: placebo or gemcabene 600 mg. Subjects will be stratified by statin intensity (as defined in Table 1) and Type 2 diabetes (yes or no). Subjects defined as diabetic will be those receiving concomitant anti-diabetic medication at screening. Randomization within a baseline statin intensity stratum will be capped at 52 subjects; once 52 subjects are randomized into a baseline statin intensity stratum, no further subjects in that statin intensity will be randomized (subjects in the other baseline statin intensity stratum will continue to be randomized until there are 52 randomized subjects in that stratum). By also stratifying on baseline diabetes

(yes, no), diabetic subjects will be evenly distributed across the treatment groups and statin-intensity subgroups. The first dose of study drug will be administered at the site on Day 1. On days with a scheduled office visit with blood sample collection, subjects will remain fasted (at least 10 hours) and should not take gemcabene until after the blood samples are collected. For days when the subject will self-dose, subjects will be instructed to take study drug at the same time in the morning with a full glass (8 ounces) of water either with or without food.

Post-randomization clinic visits will occur at Week 2, Week 4, Week 8 and Week 12. The Follow-up Visit will occur 4 weeks (± 3 days) after the last dose of study drug.

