8.1.4.2 Creatinine increase

If, at any visit, a creatinine increase >0.3 mg/dL (27 μ mol/L) from baseline or a GFR decrease of >15 mL/min from baseline is observed, a repeat chemistry will be performed. The subject's past medical history, concomitant medications (including over the counter drugs and herbal supplements), and any recent symptoms (e.g., fatigue, malaise, polyuria/oliguria, or palpitations) will be reviewed to determine a potential etiology and make a clinical assessment of the significance of the finding.

During the study, clinically significant abnormal results in NGAL will be used as a means of identifying subjects who have unremarkable creatinine/BUN values at the time of assessment but may require additional or closer/follow-up monitoring of renal studies.

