9 STATISTICS

9.1 Sample Size

The primary efficacy endpoint is the percent change from baseline to Week 12 in LDL-C, with the primary focus on the overall set of randomized subjects. The efficacy within each baseline statin intensity (high-intensity; moderate-intensity) stratum is also of interest for this study; thus, the study is powered for the analyses within each baseline statin intensity stratum. A sample size of 26 randomized subjects in the gemcabene 600 mg group and 26 randomized subjects in the placebo group within each baseline statin intensity stratum is expected to provide 80% power to detect a difference of 17% in the percent change from baseline to Week 12 in LDL-C between the gemcabene treatment group and the placebo group within each baseline statin intensity stratum. This calculation is based on a 2-sided t-test at the 5% level of significance ($\alpha = 0.05$), a common standard deviation of 20, and a drop-out rate of 10%. The sample size of 26 randomized subjects in each baseline statin intensity stratum in the gemcabene 600 mg group gives a total of 52 randomized subjects in the gemcabene 600 mg group. Twenty-six randomized subjects in each baseline statin intensity stratum in the placebo group gives a total of 52 randomized subjects in the placebo group. Thus, the total study sample size is 104 randomized subjects.

There are no planned interim analyses in the study.

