The following laboratory parameters will be summarized at baseline and at each post-baseline time point by treatment group. Additionally, CFBL to each time point (including end of treatment), if appropriate, for each of the following laboratory parameters will also be summarized by treatment group. If, for a given subject at a given visit, the absolute count of neutrophils are not provided but segmented and band neutrophils are, segmented and band neutrophils are summed to determine the absolute count of neutrophils. If only segmented neutrophils are provided, they are used as the absolute count of neutrophils. Similarly, if neutrophils/leukocytes are not provided at a given visit but neutrophils (segmented)/leukocytes are, neutrophils (segmented)/leukocytes are used as neutrophils/leukocytes. If a laboratory value is lower or higher than the detection limit, the value will not contribute to summary statistics but will be included in the listings.

- **Chemistry:** ALT, albumin, ALP, AST, bicarbonate, BUN, calcium, chloride, creatine kinase (CK), creatinine, gamma-glutamyl transferase (GGT), glucose, lactate dehydrogenase (LDH), phosphorus, potassium, sodium, (total) bilirubin, (total) protein, estimated glomerular filtration rate (GFR)
- **Coagulation:** prothrombin time, activated partial thromboplastin time, international normalized ratio
- **Hematology:** hemoglobin, hematocrit, leukocytes, basophils, eosinophils, lymphocytes, monocytes, neutrophils, platelets, red blood cell count, mean corpuscular hemoglobin concentration, mean corpuscular hemoglobin, mean corpuscular volume
- **Urinalysis:** pH, specific gravity, NGAL, creatinine, protein, protein/creatinine ratio, albumin, albumin/creatinine ratio

Out-of-range values will be assessed using shift tables. Laboratory values will be identified as low, normal, or high based on the normal ranges provided by the central laboratory. Shift tables for each parameter will display, for each treatment group, the number of subjects with low, normal, and high values at baseline and end of treatment. Additionally, a summary will be provided of the number of subjects who shifted to high or low during the study. The denominators will be the number of subjects at risk for shifting, ie, the subjects at risk for shifting to low are those with high or normal values at baseline, and the subjects at risk for shifting to high are those with low or normal values at baseline.

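### The plan describes a small mean effect of gemcabene on creatinine, BUN and GFR but pre-specifies no baseline-adjusted, placebo-corrected estimate of it with a confidence interval

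*Protocol*

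**What the plan says.** **The expected effect.** Protocol 1.3 reports small mean increases in creatinine and BUN in some earlier studies, appearing in the first 2 to 4 weeks and then not growing. It adds: "An iohexol clearance study showed that glomerular filtration rate (GFR) decreased slightly and was associated with a slight increase in serum creatinine". No magnitude or SD is given.

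**Its standing in the trial.** Both documents (Protocol synopsis, safety endpoints; SAP 6.3) give renal markers particular attention. Safety of 600 mg, overall and within each statin-intensity group, is a secondary objective (Protocol 2.2). Protocol 1.4 says the efficacy and safety data will inform Phase 3.

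**The analysis.** Protocol 9.3.2 says "No statistical analysis of safety data will be performed in this study", and SAP 12 restricts safety to descriptive statistics on observed data, by treatment received. For the renal markers, SAP 12.2 and Table 3 plan:
- values at baseline and at each later time point by arm; change from baseline, including to end of treatment, "for each of the following laboratory parameters will also be summarized by treatment group" (under SAP 9.2: mean, SD, median, minimum and maximum);
- low/normal/high shift tables by arm;
- counts of subjects with a creatinine rise above 0.3 mg/dL or an estimated GFR fall above 15 mL/min at any time after baseline, as single and consecutive occurrences, with single occurrences repeated by statin stratum;
- listings.

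The creatinine cut-off matches the repeat-testing trigger in Protocol 8.1.4.2 ("creatinine increase >0.3 mg/dL"). By contrast, continuous efficacy markers such as adiponectin and fibrinogen get a placebo-corrected LS mean with a 95% CI (Protocol 9.3.1.2).

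**The concern.** The renal effect described is a small shift in the mean. The quantity that isolates it in a randomized trial is the difference in mean change between gemcabene and placebo, and that difference needs an interval to show which sizes of effect remain compatible with the data. Neither document plans one for any safety laboratory value, and the SAP's additional manuscript analyses (Appendix 5) do not supply it.

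The threshold counts cannot stand in for it, because a fixed cut-off well above a small mean shift responds weakly to that shift. Without a pre-specified contrast, anyone who later wants a placebo-corrected renal figure for Phase 3 planning must choose the visit, population and adjustment after seeing the data.

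**Working it through.** **1. The plan's own sample-size figure.** Inputs from Protocol 9.1: "80% power to detect a difference of 17% in the percent change from baseline to Week 12 in LDL-C", "This calculation is based on a 2-sided t-test at the 5% level of significance", SD 20 and 10% drop-out. From Protocol 3.1: 1:1 allocation. By the noncentral t distribution, 22 per arm gives 78.6% power and 23 per arm gives 80.5%. Then 23 / (1 − 0.10) = 25.6, rounded up to 26 per arm per stratum, and 26 × 4 = 104. The figure reproduces. It concerns LDL-C only; no precision figure is given for any renal marker.

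**2. Precision of the missing contrast.** Half-width of the unadjusted 95% CI = t(0.975, 2n − 2) × SD × √(2/n).

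| Subjects per arm | t | √(2/n) | Half-width in SD units |
|---|---|---|---|
| 52 (all randomized) | 1.984 | 0.196 | 0.389 |
| 47 (52 × 0.90 = 46.8) | 1.986 | 0.206 | 0.410 |
| 26 (one stratum) | 2.009 | 0.277 | 0.557 |
| 23 (one stratum, after drop-out) | 2.015 | 0.295 | 0.594 |

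The SD of change is **assumed**: 0.08 to 0.15 mg/dL for creatinine and 8 to 12 mL/min for estimated GFR.

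| Subjects per arm | Creatinine half-width, mg/dL | Estimated GFR half-width, mL/min |
|---|---|---|
| 52 | 0.031 to 0.058 | 3.1 to 4.7 |
| 47 | 0.033 to 0.061 | 3.3 to 4.9 |
| 23, one stratum | 0.048 to 0.089 | 4.8 to 7.1 |

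These are unadjusted widths; adjustment for baseline would usually not widen them.

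**3. Means against threshold counts (illustration).** Assume normally distributed changes, a true creatinine shift of 0.05 or 0.10 mg/dL, four post-baseline visits and a between-visit correlation of 0.5 to 0.7. None of these values is in the documents. The count is simulated as SAP Table 3 defines it, at any time after baseline, and shown as expected subjects per 52. The last column is the probability that the interval at 47 per arm excludes zero.

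| SD | Shift | Gemcabene count | Placebo count | Interval excludes 0 |
|---|---|---|---|---|
| 0.10 | 0.05 | about 1 | 0.2 to 0.3 | 67% |
| 0.10 | 0.10 | 3.1 to 3.7 | 0.2 to 0.3 | over 99% |
| 0.15 | 0.05 | 6 to 7 | 3 to 4 | 36% |
| 0.15 | 0.10 | 10 to 12 | 3 to 4 | 89% |

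The counts depend heavily on the assumed SD. At SD 0.10 a shift of 0.05 moves the expected count by about one subject.

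**The case against.** The strongest reply is that the plan already shows the effect. SAP 12.2 prints mean and SD of change for creatinine, BUN and estimated GFR in each arm at every visit, beside concurrent placebo. A mean shift would be visible, and with the group sizes a reader could compute an unadjusted interval. **This stands**: the gap is an unplanned estimate, not lost information.

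A reader might infer that the report could show close to no threshold cases in either arm and so be taken as evidence of no renal effect. The documents do not support that. The counts sit alongside the means and do not replace them. They also run over all post-baseline visits, so near-zero counts in both arms are not the general expectation: at SD 0.10 a 0.10 mg/dL shift would give about 3 to 4 subjects on gemcabene.

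A reader might also infer that the trial is certain to bound the renal effect tightly. The documents give neither an SD nor an effect size, so the precision figures are conditional on the assumed SDs.

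Finally, descriptive-only safety is a common choice for a Phase 2 trial sized on LDL-C, and the two documents agree on it. **This also stands**: there is no contradiction and no numerical error. It does not remove the case for an interval on the one renal effect that the protocol itself describes.

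**Conclusion.** The point holds as a cheap improvement. The readable text of the plan contains no gemcabene-minus-placebo renal difference and no interval for one, although the protocol describes a mean renal effect and makes safety a secondary objective. Some exploratory text is redacted and cannot be checked, but the general statements in Protocol 9.3.2 and SAP 12 govern safety laboratory data.

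If the SD of creatinine change lies between 0.08 and 0.15 mg/dL, the added estimate would carry a margin of about ±0.033 to ±0.061 mg/dL with 47 evaluable per arm, and ±0.031 to ±0.058 with all 52. Within one statin stratum it would be about 1.45 times as wide (0.594 / 0.410). The gain over the present plan is a pre-specified choice of model, visits and population, adjustment for baseline, and uncertainty stated in print. The argument for that gain does not depend on the assumed SD; only the widths do.

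**What to change.** Keep the descriptive plan and make two changes.

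1. **SAP 12.2:** add one table for serum creatinine, estimated GFR and BUN. It gives the LS-mean difference, gemcabene minus placebo, in change from baseline with a 95% CI and no p-value, labelled descriptive, at Weeks 2, 4, 8 and 12 and at end of treatment. Use observed data in the Safety Analysis Set by treatment received, with the ANCOVA of SAP 11.1: the marker's own baseline as covariate, and statin stratum and diabetes as factors. Present it overall and, without the stratum term, within each statin stratum, to match the secondary safety objective. Note the exception in the opening paragraph of SAP 12.
2. **Protocol 9.3.2,** and the same sentence in the synopsis: reword to *No hypothesis testing of safety data will be performed.*

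**Cost.** SAP and protocol wording and one table from existing code and data; no new visits, samples or subjects. The downside is the number of unadjusted intervals: 3 markers × 5 time points = 15 overall, and 15 × 3 = 45 with both strata. The label should say that they are for estimation and that no single interval is to be read as a test.

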10 DATA MANAGEMENT AND RECORD KEEPING

10.1 Data Management

10.1.1 Data Handling

Data will be recorded at the site on eCRFs and reviewed by the CRA during monitoring visits. The CRAs will verify data recorded in the EDC system with source documents. All corrections or changes made to any study data must be appropriately tracked in an audit trail in the EDC system. An eCRF will be considered complete when all missing, incorrect, and/or inconsistent data has been accounted for.

10.1.2 Computer Systems

Data will be collected and processed using a validated EDC system. The system and procedures are designed in compliance with Title 21 of the Code of Federal Regulations (21 CFR Part 11).

10.1.3 Data Entry

Data must be recorded using the EDC system as the study is in progress. All site personnel must log into the system using their secure user name and password in order to enter, review, or correct study data. These procedures must comply with 21 CFR Part 11 and other appropriate international regulations. All passwords will be strictly confidential.

10.1.4 Medical Information Coding

For medical information, the following thesauri will be used:

- Latest version of MedDRA for medical history and adverse events, and
- World Health Organization Drug Dictionary for prior and concomitant medications.

10.1.5 Data Validation

Validation checks programmed within the EDC system, as well as supplemental validation performed via review of the downloaded data, will be applied to the data in order to ensure accurate, consistent, and reliable data. Data identified as erroneous, or data that are missing, will be referred to the investigative site for resolution through data queries.

The eCRFs must be reviewed and electronically signed by the Investigator.

10.2 Record Keeping

Records of subjects, source documents, monitoring visit logs, eCRFs, inventory of study product, regulatory documents, and other Sponsor correspondence pertaining to the study must be kept in the appropriate study files at the site. Source data is defined as all information in original records and certified copies of original records of clinical findings, observations, or other activities in a clinical study necessary for the evaluation and reconstruction of the clinical study. Source data are contained in source documents (original records or certified copies). These records will be retained in a secure file for the period as set forth in the Clinical Study Agreement. Prior to transfer or destruction of these records, the Sponsor must be notified in writing and be given the opportunity to further store such records.

11 INVESTIGATOR REQUIREMENTS AND QUALITY CONTROL

11.1 Ethical Conduct of the Study

Good Clinical Practice (GCP) is an international ethical and scientific quality standard for designing, conducting, recording, and reporting studies that involve human subjects. Compliance with this standard provides public assurance that the rights, safety, and well-being of study subjects are protected, consistent with the principles that have their origin in the Declaration of Helsinki, and that the clinical study data are credible.

11.2 Institutional Review Board/Ethics Committee

Federal regulations and the International Conference on Harmonisation (ICH) require that approval be obtained from an Institutional Review Board (IRB)/Ethics Committee (EC) prior to participation of subjects in research studies. The IRB/EC will review all appropriate study documentation in order to safeguard the rights, safety, and well-being of subjects. The study will only be conducted at sites where IRB/EC approval has been obtained. The protocol, Investigator's Brochure, Informed Consent Form (ICF), advertisements (if applicable), written information given to the subjects, safety updates, annual progress reports, and any revisions to these documents will be provided to the IRB/EC by the Investigator.

Prior to study onset, the protocol, any protocol amendments, ICFs, advertisements to be used for subject recruitment, and any other written information regarding this study being provided to a subject or subject's legal guardian must be approved by the IRB/EC.

No drug will be released to the site for dosing until written IRB/EC authorization has been received by the Sponsor, or designee.

11.3 Informed Consent

The ICF and any changes to the ICF made during the course of the study must be agreed to by the Sponsor or designee and the IRB/EC prior to its use and must be in compliance with all ICH GCP, local regulatory requirements, and legal requirements.

The Investigator, or a person delegated the responsibility by the Investigator, must ensure that each study subject (or legally acceptable representative) is fully informed about the nature and objectives of the study and possible risks associated with participation and must ensure that the subject has been informed of his/her rights to privacy. The Investigator or delegate will allow the subject adequate opportunity to read the written informed consent and ask any questions. The Investigator will obtain written informed consent from each subject before any study-specific activity is performed and should document in the source documentation that consent was obtained prior to any study-specific activity. The original signed copy of the ICF must be maintained by the Investigator and is subject to inspection by a representative of the Sponsor, their representatives, auditors, the IRB/EC and/or regulatory agencies. A copy of the signed ICF will be given to the subject.

11.4 Subject Card

On enrollment in the study, the subject will receive a subject card to be carried at all times. The subject card will state that the subject is participating in a clinical research study, type of treatment, number of treatment packs received, and contact details in case of an SAE.

